9. REPORTING ADVERSE EVENTS

9.1. Definitions

9.1.1. Adverse Event

An AE is any untoward medical occurrence in a clinical study participant administered a pharmaceutical product regardless of its causal relationship to the study treatment. An AE can therefore be any unfavorable and unintended sign (including an abnormal laboratory finding, for example), symptom, or disease temporally associated with the use of a medicinal product, whether or not considered related to the medicinal product.

9.1.2. Serious Adverse Event

A serious AE (SAE) is any untoward medical occurrence at any dose that fulfils one or more of the following:

- Results in death
- Is life-threatening, eg, the participant was, in the opinion of the investigator, at immediate risk of death from the event as it occurred (does not include an event that, had it occurred in a more severe form, might have caused death)
- Requires inpatient hospitalization or prolongation of existing hospitalization. (Note: a prescheduled hospitalization is not considered an SAE.)
- Results in persistent or significant disability or incapacity
- Is a congenital anomaly or birth defect
- Is an other medically significant event that, based upon appropriate medical judgment, may jeopardize the participant and may require medical or surgical intervention to prevent one of the outcomes listed above (eg, allergic bronchospasm requiring intensive treatment in an emergency room or home, blood dyscrasias or convulsions that do not result in hospitalization, the development of drug dependency or drug abuse)

9.1.3. Adverse Event of Special Interest

For this trial, an AESI is defined as any AE having an autoimmune etiology. Refer to [Appendix B](#) for a list of AESI terms defined by FDA's CBER that are potentially associated with autoimmune disease, and might represent a safety signal for vaccine-associated autoimmunity. Potential AESIs will be assessed by a member of the DSMB having expertise in this area (refer to [Section 8.4.1](#)). Once assessed as autoimmune in nature, the event will be considered as a confirmed AESI and recorded on the AE eCRF.

9.2. Eliciting and Reporting Adverse Events

AEs (including SAEs and potential AESIs) reported spontaneously by the participant and/or in response to an open question from the PI or designee or revealed by observation (eg, during PE or from a clinical test result) will be recorded by the PI or designee on the AE eCRF if they

occurred from the time of the first vaccination on Day 1 up to Month 13, regardless of causal association with the IP. AE reporting is required for any new observation presenting after the first vaccination or for a deterioration of baseline condition (eg, increased severity/frequency). From the signing of the ICF until immediately before the first vaccination on Day 1, only AEs resulting from a study-related procedure will be recorded on the AE eCRF; all other events reported in this time period will be recorded as signs and symptoms on the Medical History eCRF. If there is any doubt as to whether a clinical or laboratory observation is an AE, the event will be considered an AE and recorded on the AE eCRF.

Refer to the specific sections on clinical laboratory tests ([Section 8.3.2](#)), PEs ([Section 8.3.3](#)), vital signs ([Section 8.3.4](#)), and e-diary reactogenicity ([Section 8.3.5.1](#)) for details on AE reporting based on participant observation and clinical test results.

9.2.1. Rating the Severity of Adverse Events

The severity of AEs will be assessed by the PI or designee using toxicity grading (Grade 1 to 4) according to a the FDA Guidance for Industry: *Toxicity Grading Scale for Healthy Adult and Adolescent Volunteers Enrolled in Preventive Vaccine Clinical Trials* {[CBER, 2007](#)} (refer to [Appendix A](#)).

The toxicity grading scale has specific grading options for some clinical symptoms, such as nausea/vomiting, diarrhea, headache, fatigue, and myalgia. For symptoms not appearing on the grading scale, the grading for generic “illness or clinical AE” will be used (refer to [Table 8](#)). For AEs being reported from clinical assessments, the PI or designee will refer to the specific sections on clinical laboratory tests (refer to [Section 8.3.2](#)), PEs (refer to [Section 8.3.3](#)), vital signs (refer to [Section 8.3.4](#)), and e-diary reactogenicity (refer to [Section 8.3.5.1](#)) on how and when to report AEs and AE severity in applying the toxicity grading scale.

9.2.2. Rating the Causality of Adverse Events

The PI’s (or designee’s) assessment of an AE’s causal relationship to the IP will be documented on the AE eCRF. The following guidelines are provided for this assessment.

- Unrelated: no relationship between the IP and the reported event
- Possibly related: the event follows a reasonable temporal sequence from the time of administration of investigational product and/or follows a known response pattern to the IP, but could also have been produced by other factors
- Probably related: a reasonable temporal sequence of the event with administration of IP exists and, based on the known response to the IP, known or previously reported adverse reactions to the IP or similar products, or in the PI or designee’s clinical judgment the association of the event with the IP seems likely
- Definitely related: a definite causal relationship exists between the administration of the IP and the AE and other conditions (eg, concurrent illness, progression/expression of the disease state, concurrent medication reaction) do not appear to explain the event

If the relationship between the AE and the IP is determined to be “possible” or “probable” or “definitely related,” the event will be considered to be related to the IP.

9.3. Immediately Reportable Events

9.3.1. Principal Investigator’s Reporting Requirements

The following events must be reported via email immediately (eg, within 24 hours of awareness) by the PI or designee to Emergent’s Global Pharmacovigilance Department (Global PV):

- Any SAE regardless of causal association with the IP
- Any potential AESI, eg, AE of autoimmune etiology (refer to the list of AESI terms in [Appendix B](#)) regardless of causal association with the IP
- Any pregnancy where conception occurred after first exposure to the IP through Month 13

The appropriate form (listed below) will be completed and sent by email to the following address:

For SAEs and AESIs, the Serious Adverse Event and/or Adverse Event of Special Interest Report Form will be completed (abbreviated hereafter SAE Report Form, AESI Report Form). Note that the SAE and AESI report forms are not the same as the AE eCRF. Accompanying the form(s) will be source documentation or medical records (eg, discharge summary for hospitalizations, lab reports) which support a diagnosis. Participant identifiers (eg, name, address, telephone number, social security number, medical record number, or hospital/laboratory number) must be redacted from the source documentation.

All SAEs that are unexpected (eg, adverse drug reactions) must be reported to the IRB/IEC as required by ICH GCP E6.

Confirmed pregnancies where conception occurred after first exposure to the IP through Month 13 will be reported to Global PV using the Pregnancy Notification Form. Although normal pregnancy is not an AE, it will mandate discontinuation of IP (refer to [Section 9.4](#)).

9.3.2. Sponsor’s Reporting Requirements

A SUSAR is a suspected adverse reaction that is both serious and unexpected. As specified in 21 CFR 312.32, SUSARs will be reported by the Sponsor of the Investigational New Drug Application (IND) to the FDA and to all participating PIs in an IND safety report as soon as possible, no later than 15 calendar days after the Sponsor becomes aware of the suspected adverse reaction (21 CFR 312.32(c)(1)).

In addition, any unexpected fatal or life-threatening suspected adverse reaction will be reported to FDA no later than seven calendar days after the Sponsor's initial receipt of the information (21 CFR 312.32(c)(2)).

The Sponsor will additionally report AESIs to FDA within 15 days after becoming aware of the AESI.

9.4. Pregnancy

Women of childbearing potential must use an effective method of birth control from at least one month prior to Day 1 through Month 13. Methods of acceptable birth control are listed in [Section 5.2](#).

Prior to trial enrollment, participants must be advised of the importance of avoiding pregnancy during trial participation and the risks of an unintentional pregnancy. The participant must sign an ICF stating that the risk factors and consequences were communicated.

Pregnancy testing will be conducted at Screening and at specified time points during the study through Day 64/EWV (refer to [Section 8.1](#)). If a participant becomes pregnant between Screening and Day 1 prior to randomization, no IP is to be administered (refer to [Section 8.1.2](#)).

During the trial, all WOCBP will be instructed to contact the PI immediately if they suspect they might be pregnant (eg, missed or late menstrual cycle). Female participants must have a negative urine pregnancy test before receiving any vaccination. If the test is positive, vaccination will be suspended pending the outcome of a serum pregnancy test. Once pregnancy is confirmed, no further IP is to be administered to the participant. Participants will be encouraged to continue planned safety follow-up in the study. (Note, if the serum pregnancy test is negative, the vaccination visit may be rescheduled if it falls within the visit window for the visit, else the participant is to be discontinued from further vaccinations.)

If a participant becomes pregnant after the first vaccination, the investigational site staff will report the pregnancy to Emergent within 24 hours of awareness by completing the Pregnancy Notification Form and forwarding it to Global PV (refer to [Section 9.3](#) for details). The Sponsor will forward a Pregnancy Outcome Form to the investigational site for monitoring the outcome of the pregnancy, including perinatal and neonatal outcomes. Separately, the PI or designee must also notify the IRB/IEC.

All pregnancies where conception occurred after first exposure to the IP through Month 13 are to be followed to outcome (eg, delivery, spontaneous/elective/therapeutic abortion), including after the study is completed and even if the participant is withdrawn from the study. When the PI or designee becomes aware of the outcome of the pregnancy, a Pregnancy Outcome Form will be completed and forwarded to the Global PV Department within 24 hours of awareness. While pregnancy itself is not considered an AE, pregnancy outcomes of spontaneous miscarriage, congenital anomaly, or birth defect are considered to be SAEs and must be reported according to the procedures described in [Section 9.3](#). Elective abortions without complications will not be handled as AEs. As applicable, contact will be made when the infant is approximately 28 days old for a final follow-up, also reported on the Pregnancy Outcome Form.

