Because of this potential risk, the enrollment of individuals with a history of autoimmune disorders or active autoimmune disease will be prohibited in the current trial. Additionally, because of the possibility for a delay between the vaccination and onset of symptoms indicative of a disease process, all participants will be followed for potential adverse events of autoimmune etiology up to Month 13 (nominally for 12 months after the last vaccination). Such AEs will be captured as "adverse events of special interest [AESI]" referring to the list of autoimmune disorders compiled by CBER and listed in [Appendix B](#). Blood samples will be collected at specified time points from all participants for auto-antibody testing. Participants who discontinue study treatment will be encouraged to attend all subsequent clinic visits and safety follow-up contacts to facilitate this monitoring.

Pregnancy and Lactation

No reproductive toxicity studies have been performed with AV7909. BioThrax can cause fetal harm when administered to a pregnant woman {[BioThrax Prescribing Information, 2015](#)}. CPG 7909 had been determined to be embryo-lethal in rabbits and teratogenic in developing rats and rabbits at doses far in excess of the individual vaccination dose for anthrax PEP (0.25 mg). In rats, fetal skeletal anomalies were noted (>3 mg/kg/day); in rabbits, slightly reduced numbers of viable fetuses (3 mg/kg/day), and external, visceral, and skeletal malformations occurred (>1 mg/kg/day).

Consequently, breastfeeding and a positive pregnancy test will preclude study enrollment. All women of childbearing potential must additionally have a negative pregnancy test before each vaccine administration, and must use effective contraception from at least one month prior to Day 1 and continued through Month 13. Confirmed pregnancy will result in discontinuation of vaccinations. Participants must be monitored for pregnancy outcomes according to protocol-specified procedures.

Injections

Potential risks associated with both IM and SC injections include nerve or blood vessel damage, dizziness, fainting, infection, sterile abscess, and pain associated with a needle stick. Potential risks associated with venipuncture include pain/tenderness, swelling, bleeding, bruising, dizziness, and infection.

Refer to the Investigator's Brochure for further details.

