12. QUALITY CONTROL AND QUALITY ASSURANCE

12.1. Monitoring

The site will be monitored at regular intervals using a risk-based monitoring approach to ensure compliance with the protocol, ICH GCP, applicable regulatory requirements, and current SOPs of the CRO and Emergent. Sites will be monitored both remotely and in-person to ensure the integrity of the data collection and the safety of study participants. A medical monitoring plan will be established, and data will be reviewed on a monthly basis. A Monitoring Plan containing the frequency of on-site and remote monitoring visits conducted by the CRO study monitors as well as monitoring requirements and contact details of the CRO study monitors will be developed and followed throughout the study. Blinded and unblinded CRO study monitors will be designated responsibilities according to the Monitoring Plan. Emergent personnel (blinded and unblinded) will perform oversight of the CRO monitoring function.

As a representative of Emergent, the CRO study monitors will visit the site periodically. In addition, the CRO study monitors will be available between visits via telephone and email as needed. The CRO study monitors will perform the following functions:

- Provide information and support to the PI(s)
- Confirm the facility(-ies) are satisfactory to continue study conduct
- Confirm the site is adhering to the protocol, data are being accurately recorded in the eCRFs, and IP accountability checks are being performed
- Perform source data verification including a comparison of eCRF data with the participant's clinic records and other records relevant to the study. This will require direct access to all original records for each participant (eg, clinic charts).
- Confirm that the e-diaries have been properly completed and reviewed by site personnel
- Record and report any protocol deviations not previously sent to Emergent
- Confirm AEs, AESIs, SAEs, and pregnancies have been properly documented (eCRF, SAE/AESI Report Form) and reported (sponsor, IRB/IEC)
- Confirm all pregnancies where conception occurred after first exposure to the IP through Month 13 are followed properly and that the post-birth follow-up occurs

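### Pregnancy notification and outcome follow-up are limited to conceptions after first exposure, so a pregnancy already present but undetected at dose 1 falls outside the literal rules

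*Protocol*

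**What the plan says.** Four places in the protocol tie the pregnancy rules to the date of conception.

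- Section 9.3.1, list of immediately reportable events: "Any pregnancy where conception occurred after first exposure to the IP through Month 13".
- Section 9.3.1, Pregnancy Notification Form: "Confirmed pregnancies where conception occurred after first exposure to the IP through Month 13 will be reported to Global PV".
- Section 9.4, outcome follow-up: "All pregnancies where conception occurred after first exposure to the IP through Month 13 are to be followed to outcome". The same sentence extends follow-up beyond the end of the study and beyond withdrawal.
- Section 12.1, monitor's follow-up bullet: "Confirm all pregnancies where conception occurred after first exposure to the IP through Month 13 are followed properly".

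A fifth place uses a different trigger. The notification sentence in Section 9.4 reads "If a participant becomes pregnant after the first vaccination, the investigational site staff will report the pregnancy to Emergent within 24 hours of awareness", and points to Section 9.3 for details.

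For the period before Day 1, the protocol relies on preventing the dose. There is a serum test at Screening, a urine test on Day 1 and a contraception requirement from at least one month before Day 1 (Sections 5.1 and 5.2). Section 9.4 adds: "If a participant becomes pregnant between Screening and Day 1 prior to randomization, no IP is to be administered".

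**The concern.** The rule on pregnancy before Day 1 works only if the pregnancy is known. Consider a woman who conceives shortly before Day 1, tests negative that day, is vaccinated, and has a confirmed positive test on Day 15. Vaccination stops. The vaccine reached an existing pregnancy, but conception came before first exposure, so none of the four conception-based triggers is met.

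This sits badly with the protocol's own reasons for tracking pregnancies. Section 2.3.2 states that "BioThrax can cause fetal harm when administered to a pregnant woman", that no reproductive toxicity studies have been done with AV7909, and that CPG 7909 was embryo-lethal or teratogenic in animals, at doses far above the vaccine dose. The rules require follow-up of a pregnancy conceived nominally up to 12 months after the last vaccination, but not of one present when the vaccine was given.

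**Working it through.** **1. Does any passage cover the case?** The pregnancy text of both documents, set against a pregnancy present but undetected at dose 1:

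| Place | Scope | Covers the case? |
|---|---|---|
| Protocol 9.3.1, reportable events | Conception after first exposure | No |
| Protocol 9.3.1, Notification Form | Conception after first exposure | No |
| Protocol 9.4, notification sentence | Becoming pregnant after the first vaccination; refers to 9.3 | Unclear; 9.3 uses conception |
| Protocol 9.4, outcome follow-up | Conception after first exposure | No |
| Protocol 12.1, follow-up bullet | Conception after first exposure | No |
| Protocol 12.1, preceding bullet | Pregnancies documented and reported, no conception limit | Yes, for documentation and reporting; sets no follow-up duty |
| Protocol 2.3.2 | Pregnancy outcomes to be monitored, no date limit | Defers to the protocol's procedures, which carry the limit |
| Protocol 9.1.2 and 9.4, SAEs | Miscarriage, congenital anomaly, birth defect; no conception limit | Yes, if the site learns of the outcome |
| SAP 7.7.5 | Listing of test results for participants with a positive result | Test results only, no outcomes |

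No passage requires notification and follow-up to outcome for this case.

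**2. How could a pregnancy be missed?** The Screening serum test is 2 to 28 days old at Day 1 (Section 8.1.1), so the urine test is the last check. The documents give no detection limit for it. The length of the undetected window is therefore an assumption, taken here as 7 or 14 days.

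**3. How many?** The plan gives no figure to reproduce. The only input from the documents is N = 3850. The WOCBP share (30-50%) and the annual conception rate on contraception (1-6%) are assumptions.

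Expected number = 3850 × share × rate × window/365

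| Share, rate | 3850 × share × rate | × 14/365 | × 7/365 |
|---|---|---|---|
| 30%, 1% | 11.55 | 0.44 | 0.22 |
| 40%, 3% | 46.2 | 1.77 | 0.89 |
| 50%, 6% | 115.5 | 4.43 | 2.22 |

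For comparison, conceptions from Day 1 to Day 394 under the same assumptions run from 11.55 × 394/365 = 12.5 to 115.5 × 394/365 = 124.7. At a constant rate, the uncovered group is 14/(14 + 394) = 3.4% of all exposed or later pregnancies, or 7/(7 + 394) = 1.7% with the shorter window, whatever the share and rate.

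**4. Would scheduled contacts catch the outcome anyway?** Assume 266 days from conception to term (not in the documents). A conception k days before Day 1 delivers on about Day 1 + 266 − k. That is Day 266 for k = 1 and Day 253 for k = 14. Both fall between the Month 7 call (Day 211 ± 14) and the Month 10 call (Day 302 ± 14). The infant reaches 28 days on about Days 281 to 294, well before the Month 13 call (Day 394 ± 14).

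**The case against.** The strongest reply is that little is lost in practice, and much of it stands.

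- **A reader might infer that a birth defect in such a pregnancy would never come to light. The documents do not support that.** Section 8.1.8 schedules calls at Months 4, 7, 10 and 13 that ask about SAEs and, for WOCBP, possible pregnancies. On the dates above, delivery falls inside that schedule. Miscarriage, congenital anomaly and birth defect are SAEs whatever the conception date (Sections 9.1.2 and 9.4), reportable within 24 hours regardless of causality (Section 9.3.1).
- **Nor would the sponsor be unaware of the pregnancy.** Urine results go into the eCRF (Table 6), pregnancy is a listed reason for stopping vaccination (Table 5), and a separate bullet in Section 12.1 has monitors confirm that pregnancies are documented and reported.
- **The notification sentence in Section 9.4 might be read leniently**, dating pregnancy from detection rather than conception. That is possible, but it refers to Section 9.3, which uses conception, as does the outcome rule.
- **Contraception, two tests before dose 1 and a test before every later dose make the case rare.** They do. The scheme of repeated testing nevertheless assumes that contraception can fail.
- **It is tempting to state flatly that the urine test cannot detect a conception in the preceding one to two weeks.** The documents give no sensitivity, so this remains an assumption. The gap exists for any pregnancy the test misses.

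The reply does not restore what Section 9.4 assures for other pregnancies. SAE reporting and calls depend on the participant staying reachable and mentioning the event, and they do not record normal outcomes or uncomplicated elective abortions.

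**Conclusion.** The concern holds in a limited form. Sections 9.3.1, 9.4 and the follow-up bullet in 12.1 leave a pregnancy present but undetected at dose 1 outside required notification and follow-up to outcome. The notification sentence in 9.4 also uses a trigger that does not match the others.

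Three things are lost: the required Pregnancy Notification Form, assured follow-up to outcome after withdrawal or study end, and the normal outcomes and uncomplicated elective abortions needed as a denominator. Withdrawal matters most, because on the assumed gestation a term delivery precedes Month 13.

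The expected number is about 0.4 to 4.4 with a 14-day undetected window and 0.2 to 2.2 with 7 days. The window, the WOCBP share and the conception rate are all assumptions, and the calculation treats every conception in the window as missed. That the text leaves the case out does not depend on these figures.

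A reader might take the animal findings in Section 2.3.2 as evidence of harm at the vaccine dose. The protocol places them at doses far above it, so they support collecting the outcomes and no more. No immunogenicity endpoint, analysis population or hypothesis test is affected.

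**What to change.** Make two coordinated wording changes so that all five places agree.

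1. In Section 9.3.1 (both places), the outcome rule in Section 9.4 and the follow-up bullet in Section 12.1, replace the clause limiting scope to conception after first exposure with: *ongoing at, or conceived after, first exposure to the IP, through Month 13*.
2. The notification sentence in Section 9.4 does not contain that clause, so it needs its own edit. Begin it: *If a participant is found to have been pregnant at, or becomes pregnant after, the first vaccination*.

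The cost is a wording amendment in three sections and, on the assumptions above, a few more pregnancies followed with existing forms. It adds no visits or tests and does not change dosing or the criteria for stopping vaccination.
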